- CPRS Research Note/Reminders: The MTG tool creates a provider reported that will be cut and pasted into CPRS as a research note to summarize and communicate to the patient's PACT team the weight management discussions and initial goals agreed on between the patient and health coach. It includes the patient's self-reported BMI, risk-level, importance/confidence in controlling weight, level of social support, weight loss goal and SMART nutrition and physical activity goals, barriers, current behaviors, and interested VA resources. Completion of this note generates a reminder within CPRS for the PCP or RN care manager to read the research note, document whether they discussed the goals, resources, and barriers, and also document any additions or changes to the weight management plan. This research note and reminder system will also be used to document Health Coach telephone counseling as well as subsequent primary care visits by the patient.
- Developing telephone counseling model: The U.S. Preventive Services Task Force recommends providing more than

monthly counseling sessions within the first three months. To increase the likelihood of achieving meaningful patient weight loss, we will incorporate 10-15 telephone counseling sessions over 12 months. Most successful PC-based counseling interventions have between 5-16 interactions within a 9-12 month period. Health Coaches will be trained to call to review the patients' goal and personalized advice, monitor goal adherence, set new goals when appropriate, and use motivational interviewing techniques to address barriers to behavior change. This is an optimal way to increase the impact of the intervention since higher frequency interventions are associated with better weight loss outcomes and frequent goal setting is more effective. Further, telephone contact may be just as effective as face-to-face contact and is more cost-effective. Increasing the proportion of telephone visits is one of the T21 transformational initiatives and will become standard of care. A subset of participants will receive video conferencing calls instead of traditional telephone counseling to assess feasibility of this method of interaction as well.

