**C. RESEARCH DESIGN AND METHODS**

**OVERVIEW**

The first 10-12 participants in the MTG intervention will not be randomized to ensure that the intervention can be implemented within PACT. We will then conduct a randomized, controlled pilot study in the VA NYHHS primary care clinic to test the feasibility of implementation and acceptability of the MOVE! Toward your Goals (MTG) intervention for patients and providers. There are two distinct phases of the randomized intervention: Pilot Phase 1 and Pilot Phase 2. We will assess intermediate (e.g. self-efficacy, goal attainment, motivation to lose weight), behavioral (diet and physical activity) outcomes, and weight loss at 3, 6, and 12 months. Pilot Phase 2 is a continuation of Pilot Phase 1, however the methods of recruitment and sequence of events will be modified to maximize ease and enrollment.

In both phases, we will train participating PACT teamlets and health coaches to facilitate goal setting and conduct motivational interviewing to facilitate goal setting and conduct brief telephone counseling so that they can deliver the intervention. We will recruit primary care patients and randomize to either receive the MTG intervention or Enhanced Usual Care. On the first Baseline study visit, all participants will complete a Baseline Survey and obtain weight and height measurements.

Those in the MTG intervention group will then complete the MTG tool on a tablet computer, receive a binder of personalized materials generated by the tool, and receive a 15-20 minute counseling session about weight loss and lifestyle goals with a Health Coach (research team member). Participants randomized to the Enhanced Usual Care control will receive a handout about local MOVE!

programs and selected VA MOVE! and Healthy Living Message handouts related to weight management.

After this Baseline study visit, participants in the MTG intervention group will receive 10-15 follow up counseling phone calls with the health coach to review goals over a 12 month period. In Pilot Phase 1, participants will meet with their PCP during their regularly scheduled visit before taking an exit survey. In Pilot Phase 2, participants will meet with their PCPs at any point during the course of the one year intervention. During the visit, RN care managers and the PCPs will be prompted in CPRS to read a CPRS Research Note entered by a Health Coach. It will summarize the

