- *Providers, RN Care Managers, and other VA employees:* VA employees who participate in the study may gain improved obesity-related knowledge and patient counseling skills, which could enhance their career, job performance, and satisfaction. Specifically, VA employees may have the opportunity to receive (additional) training in 5As weight management counseling and practice brief motivational interviewing. Training in these could help to facilitate and/or improve discussions around weight management and health behavior change with patients, as well as encourage the use of individualized techniques to improve diet and exercise and setting health behavior change goals with patients.

Risk:

- *Patients:* This research involves minimal risk for physical, psychological, social, and economic harm. The researchers understand that exploration of these topics and a persons' individual struggle with their weight can be emotionally charged for many people, particularly considering the stigma placed on obesity in our society. The researchers have been trained in order to effectively facilitate conversations on this sensitive topic and will seek to minimize any emotional discomfort you may feel during the study. Additionally, any potential behavior changes related to diet or exercise will be assessed and approved by properly trained individuals including select research staff, the Primary Investigator, and health professionals. Patients will be encouraged to slowly increase their physical activity under the supervision of their PCP. While there is always the risk of injury from starting or increasing physical activity, the benefits usually outweigh potential harms. We will monitor patients for adverse events.
- *VA employees:* This research involves minimal risk for physical, psychological, social, and economic harm.

- **MEASUREMENTS**

Assessment will occur at the following time points:

- A. Baseline study visit: Baseline survey and basic physical measurements (weight, height, waist circumference)
- B. In-person follow-up study visits at 3, 6 and 12 months: Follow-up in-person questionnaire and basic physical measurements (weight, height, waist circumference)

- C. Follow-up telephone calls (only patients in MTG intervention): Follow-up telephone questionnaire

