- D. Chart review: This will occur periodically to assess MOVE! attendance, PACT teamlet visits (documentation of weight management-related conversations), and medical co-morbidities. Outcomes will be assessed through chart review up to 2 years after the baseline visit.

Baseline Data: Prior to the intervention, patients will receive a Baseline survey. To evaluate recruitment for the intervention, baseline data including socio-demographic information, perceived health status, health literacy, perceived environmental factors, and depression will be collected. Co-morbidities will be determined through chart review of the electronic medical record. We will also collect health-related attitudes, beliefs, and baseline behaviors.

Weight & Height: Study personnel will obtain patient weight measurements using a standardized protocol which includes; 1) weighing before eating without shoes or heavy garments using a digital scale that will be calibrated monthly; 2) measuring height using the primary care clinic stadiometer and rounded to the nearest half inch, at each study time point (Baseline, 3, 6, and 12 months).

Waist Circumference: Waist circumference will be measured using procedures adapted from National Health and Nutrition Examination Survey (NHANES). Study personnel will use measuring tape to the nearest 0.1cm at the high point of the iliac crest at minimal respiration. This will be measured at baseline, 3, 6, and 12 months.

Feasibility: We will use process measures (from direct observation, to determine the feasibility of implementing the MTG intervention at the initial visit. Data on time to complete the MTG tool, number and types of goals made, number of patients reporting that their PACT teamlets engaged in goal setting conversations, number of reminders completed by the PACT teamlets, time spent doing the intervention, the impact of the intervention on workflow (physician and RN Care Manager report, qualitative interviews) will be collected. At 3 and 6 months into the study period, participating PACT teamlet staff will complete an attitudes survey based on one we have used previously pertaining to intervention implementation. We will also perform qualitative interviews with RN Care Managers and providers. We will use chart review to note the number of times patients in the telephone support arm actually receive telephone counseling.

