Other Quality Control Procedures: The study staff will meet biweekly for the duration of the study to review patient recruitment and data collection procedures to ensure standardization. Research assistants will send reminders to Health Coaches when it is time to call patients in the telephone support arm. To monitor for and address unanticipated adverse events, there will be discussions during meetings with research staff, PI, mentors of PI, and providers/VA staff.

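### Adverse-event monitoring is promised but no collection item is described, and only the MTG arm has coach calls, so activity injuries may be captured unequally and may be missed in controls

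*Combined protocol and SAP*

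**What the plan says.** Four parts of the protocol bear on this point.

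- **Potential Benefit/Risk, Patients.** The text names one physical risk and makes a general promise to watch for adverse events (the quote stops just short of naming them): "While there is always the risk of injury from starting or increasing physical activity, the benefits usually outweigh potential harms. We will monitor patients for". The promise is not limited to one arm or one type of event. It comes with no definition, form or schedule.
- **Other Quality Control Procedures.** This is the only place that describes how the monitoring is done: "To monitor for and address unanticipated adverse events, there will be discussions during meetings with research staff". The sentence goes on to include the investigator, the investigator's mentors, and providers or other VA staff.
- **Measurements.** Both arms have the same three post-baseline visits: "In-person follow-up study visits at 3, 6 and 12 months: Follow-up in-person questionnaire and basic physical measurements". One further assessment is for one arm only: "Follow-up telephone calls (only patients in MTG intervention): Follow-up telephone questionnaire". The scope of chart review is stated as follows: "This will occur periodically to assess MOVE! attendance, PACT teamlet visits (documentation of weight management-related conversations), and medical co-morbidities". Adverse events are not mentioned in any of these items. Nor do they appear in the list of survey domains under 5As Intervention Development, or in the paragraphs on feasibility, acceptability, intermediate and behavioral outcomes and fidelity.
- **Overview, and Developing telephone counseling model.** After baseline, "participants in the MTG intervention group will receive 10-15 follow up counseling phone calls with the health coach to review goals" over 12 months. On these calls the coaches are to "monitor goal adherence, set new goals when appropriate, and use motivational interviewing techniques to address barriers to behavior change".

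The Data Analysis section compares intermediate, behavioral and weight outcomes between arms. It contains no summary of harms.

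**The concern.** The plan foresees a specific injury risk, encourages patients to raise their activity, and commits to monitoring. It then describes no step at which anyone asks a patient about an injury. If nothing prompts a report, the record depends on what patients happen to mention and to whom, and the two arms differ widely in how often they speak to research staff.

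The content of the calls adds to this. An injury is an obvious barrier to an activity goal, and barriers are what the coach is there to discuss. The coaches are research team members, the group that takes part in the meeting discussions, and their calls are documented in CPRS. The instruction to contact the PCP if a serious issue arises appears in the description of the MTG arm but not in that of Enhanced Usual Care.

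Two things are at stake. The first is patient safety monitoring, because an injury in a control patient may never reach the study team. The second is any injury count by arm that this pilot hands to the planned multicenter trial. An event that was never elicited cannot be recovered at analysis.

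**Working it through.** The plan states no figure on this point, so there is none to reproduce. The check is a comparison of passages, a count of contacts, and a bounded illustration.

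**1. Promise against procedure.**

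| Element | Described? |
|---|---|
| Named physical risk (activity injury) | Yes, Potential Benefit/Risk |
| Commitment to monitor | Yes, same place, all patients and all event types |
| Review forum | Yes, staff meetings, worded for *unanticipated* events |
| Question or form that elicits events | None described |
| Adverse-event field in chart review | None described |
| Harms summary in the analysis plan | None |

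An injury that the protocol itself foresees is not, on a literal reading, unanticipated. The two sentences therefore need to be reconciled.

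**2. Scheduled research contacts after baseline.** Inputs: 3 visits in each arm (Measurements and the two arm descriptions); 10-15 calls in MTG (Overview); no calls in Enhanced Usual Care (Measurements).

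- MTG: 3 + 10 = 13, up to 3 + 15 = 18
- Enhanced Usual Care: 3
- Ratio: 13/3 = 4.3, up to 18/3 = 6.0

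**3. Adding primary care visits.** The Specific Aims and Background give an average of 3.6 primary care visits per year for Veterans. Assume that this average applies equally to both arms.

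- MTG: 13 + 3.6 = 16.6, up to 18 + 3.6 = 21.6
- Enhanced Usual Care: 3 + 3.6 = 6.6
- Ratio: 16.6/6.6 = 2.5, up to 21.6/6.6 = 3.3

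The imbalance shrinks but does not disappear.

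**4. What unequal capture could do (assumed figures).** The documents give neither an injury rate nor a detection rate. If the true injury proportion p is the same in both arms and the detected fractions are d1 (MTG) and d0 (control), the apparent risk ratio is (p × d1)/(p × d0) = d1/d0. The true rate cancels out. Assume d1 between 0.9 and 1.0 and d0 between 0.3 and 0.7:

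- smallest ratio: 0.9/0.7 = 1.29
- largest ratio: 1.0/0.3 = 3.33
- if detection is equal: 1.0

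With 160/2 = 80 per arm and an assumed p of 10%, there are 8 true injuries in each arm. The record would show 7.2 to 8.0 in MTG and 2.4 to 5.6 in controls. These figures show the direction and form of the problem. They do not estimate it, because the number of contacts does not give the probability of detection.

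**The case against.** The strongest reply has five parts.

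- **The calls are not an adverse-event channel.** Nothing designates them as one. Their described content is goals, adherence and barriers, and the content of the telephone questionnaire is not given. This stands. A reader might infer that the plan collects adverse events through coach calls; the documents do not say so. The claim can only be that the calls give more opportunity for a spontaneous report.
- **Providers are part of the review.** They join the meeting discussions, and patients in both arms see them. This stands too. Controls have a route other than the study visits, and step 3 of the working allows for it. It remains an unprompted route.
- **The questionnaires are not reproduced.** An adverse-event item might be in them. The absence of an item therefore cannot be proved, only the absence of a description. The list of survey domains is fairly full, however, and adverse events are not on it.
- **The promise is broader than the meeting sentence.** A reader might infer that foreseeable injuries are deliberately left out of monitoring. The risk section contradicts that reading, because its commitment covers adverse events in general. What remains is that the broad commitment has no method and the one stated method has narrower wording.
- **No harms comparison is planned.** Safety is not an aim, the risk is described as minimal, and patients with conditions that limit activity are excluded. This limits the consequences. It does not answer the monitoring question, since the protocol itself makes the promise.

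**Conclusion.** The point holds as a gap in monitoring with a likely asymmetry between arms. The protocol names activity injury as a risk and promises monitoring, but the only procedure it describes is discussion of unanticipated events, and it describes no item that elicits events in either arm. Scheduled research contact after baseline is 13-18 in MTG against 3 in controls, a ratio of 4.3 to 6.0. The ratio falls to about 2.5 to 3.3 if both arms have the average number of primary care visits. Injuries may therefore be captured unequally and may be missed in controls.

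The conclusion assumes that the unreproduced questionnaires contain no adverse-event item and that more contact brings more spontaneous reports. Both are reasonable but neither is shown. The size of any bias cannot be derived from the documents.

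A reader might go further and conclude that the trial's results are compromised or that a planned safety comparison is invalid. The documents do not support this: no such comparison is planned, and the weight and behavioral conclusions are untouched. The effect is confined to safety monitoring and to any injury record by arm that is used in designing the larger trial.

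**What to change.** 1. Add one adverse-event item, worded identically for both arms, to the existing 3-, 6- and 12-month in-person questionnaires. It should cover injury, emergency or hospital care, and any new condition since the last visit.
2. Add fields for injury and for emergency or hospital visits to the existing chart abstraction in both arms. Coach calls are themselves documented in CPRS, so the abstraction should not count events found only in those notes; otherwise the asymmetry returns through the chart.
3. Base any summary of harms by arm on these two symmetric sources, and list events heard only on coaching calls separately.
4. Reconcile the meeting procedure under Other Quality Control Procedures with the commitment under Potential Benefit/Risk by deleting *unanticipated*.

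The cost is one question and two abstraction fields on contacts already planned, with no new visits. Visits and abstraction take slightly longer, and MTG events reported only on calls fall outside the headline summary by arm, although they stay on record. For patients already past a visit when the change is made, only the chart fields can be applied; chart review runs to 2 years after baseline, so part of the record can still be recovered.

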## • DATA ANALYSIS

Sample Size and Power Analysis: For weight loss outcomes, we will evaluate pre- and post-intervention in each arm separately and compare two arms. We base our sample size on within-person weight change at baseline and 12 months in each arm. Assuming a mean weight change of at least -2.3kg (SD=5.3) in the MTG intervention arm and no weight change in the Enhanced Usual Care arm, based on a PC-based study of clinical support tools for lifestyle change and a systematic review of technology-assisted weight loss interventions in primary care. Having 60 patients in each arm, the power is 82% to detect this pre- and post-intervention difference in each arm (at the two sided 0.05 significant level). We will also explore weight loss differences between two arms. We do not know how much additional weight loss that telephone support will lead to compared with the enhanced usual care arm. However, if we have 60 patients in each arm and assume the same SD in the weight change, we will have 80% power to detect a 2.8 kg difference between two arms. Assuming 25% dropout rate, we will randomize 160 subjects to obtain 120 evaluable subjects. We conducted sample size calculation using PASS 2008 software.

Statistics Analysis Plan: First, all the variables will be summarized using mean with standard deviation and median with interquartile range for continuous variables and frequency table for categorical variables, overall and by randomized arms, respectively. Mann-Whitney tests for continuous variables and Fisher exact tests for categorical variables will be used to check if baseline characteristics are balanced between two arms. Second, Mann-Whitney tests for continuous outcomes and Fisher exact tests for categorical outcomes will be used to compare outcome variables (including

intermediate outcomes, behavioral outcomes, and weight outcomes) between two arms at 3 months, 6 months, and 12 months, respectively. Wilcoxon rank tests for continuous outcomes and McNemar tests for binary outcomes will be used to compare them between follow-ups and baseline within each arm. Third, repeated measures modeling based on mixed models will be conducted to compare outcome variables between two arms, utilizing all the data at baseline and three follow-ups. Such modeling can adjust for baseline characteristics, take into account the correlation among repeated measures within subjects, and deal with missing data automatically assuming missing at random. Finally, we will conduct sensitivity analysis based on multiple imputation procedure to examine the impacts of missing data under some missing not at random assumptions.

We will conduct several statistical analyses to describe Veterans participating in the study. Descriptive statistics, including numerical summaries, frequency tables and graphical displays, will be used to present baseline participant characteristics. Exploratory tests, such as chi-square tests and t-tests, will be used to investigate if baseline characteristics are balanced between two randomized arms. Analysis of missing data due to dropout or incomplete surveys will be investigated by inferring a relationship between baseline characteristics/risk factors and 0-1 indicator that defines whether or not a measurement is observed. This analysis will help to identify factors that are likely to be associated with dropout. Additionally, we will investigate whether the dropout rates are different between two arms. For instance, participants with higher levels of motivation may be more likely to be retained in the study. To deal with these missing, we will incorporate the multiple imputation procedure with the regression analyses to be discussed in the following, along with some sensitivity analysis.

Qualitative Data: The audio recordings of provider interviews and patients visits will be transcribed by a VA-contracted transcription company (methods used in our previous IRB-approved study MIRB 01333). We will use detailed grounded theory-based procedures including open, axial, and selective coding. After multiple readings of the transcripts and making marginal notes with a second researcher, we will develop, test, and refine a systematic coding scheme of themes and sub-themes, and relationships thereof using NVIVO qualitative data analysis software accessed through VINCI to assist in data analysis and interpretation. Analysis will be facilitated through constant comparison techniques.

- **EXPLORATORY AIM**

Exploratory Aim: To compare the intervention arm to a third study arm of non-enrolled PC patients matched for age, gender, and BMI (“Usual Care”).

Analyzing the Third Arm: We will compare the two randomized study arms (Enhanced Usual Care and MTG intervention) arms with the third study arm of non-enrolled PC patients who are from the same cohort (seen by the same providers and eligible according to the same inclusion and exclusion criteria). Because the third study arm is not randomized, we do not expect the three arms are balanced at baseline characteristics and comparable. We will first identify important confounders (such as age, gender, BMI) and then use propensity score to adjust for these confounders when comparing the outcomes between three arms.

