During the development phase of this project, we developed a primary care-based intervention called MOVE! Toward Your Goals (MTG) to facilitate weight management within primary care and increase adoption of intensive VA programs such as MOVE!. The MTG intervention uses a new MTG software tool (that we developed) delivered on tablets to facilitate 5As-based weight management counseling with a health coach and healthcare team to promote goal-setting, behavior change, and weight loss in the primary care setting. The Veteran also receives follow up with 10-15 health coaching calls over 1 year.

As part of a pilot study for a larger, multicenter trial, we will randomize 160 subjects to receive either Enhanced Usual Care or the MTG Intervention.

**Primary Aim:** To explore differences in feasibility, acceptability, and intermediate, behavioral, and weight loss outcomes at 3, 6 and 12 months pre- and post-intervention between the MTG intervention and Enhanced Usual Care. We will explore differences within each arm and compare the 2 intervention arms.

**Hypothesis:** Among obese VA PC patients in an urban primary care practice, a brief, interactive computer-assisted intervention will result in significant improvements in intermediate (self-efficacy, intention, and motivation to change lifestyle behaviors), behavioral (diet and physical activity improvements, adherence to MOVE!), and weight loss outcomes at 3, 6 and 12 months.

**Exploratory Aim:** To compare the intervention arm to a third study arm of non-enrolled PC patients matched for age, gender, and BMI ("Usual Care").

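### The sample size rests on within-arm weight change: its stated 82% power does not reproduce (about 91%), and power for the randomised comparison at the implied 2.3 kg (about 65%) is not given

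*Combined protocol and SAP*

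**What the plan says.** Under Data Analysis, Sample Size and Power Analysis, the basis for the sample size is given as: "We base our sample size on within-person weight change at baseline and 12 months in each arm". The inputs are "a mean weight change of at least -2.3kg (SD=5.3) in the MTG intervention arm and no weight change in the Enhanced Usual Care arm". With 60 patients per arm and a two-sided 0.05 level, "the power is 82% to detect this pre- and post-intervention difference in each arm".

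The comparison of arms comes next: "We will also explore weight loss differences between two arms". The section says the extra loss over Enhanced Usual Care is not known, and that with the same SD and 60 per arm "we will have 80% power to detect a 2.8 kg difference between two arms". Allowing for 25% dropout, 160 are randomised to give 120 evaluable.

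The Statistics Analysis Plan lists three kinds of analysis for weight:

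- Mann-Whitney tests between arms at 3, 6 and 12 months;
- Wilcoxon tests for continuous outcomes, which "will be used to compare them between follow-ups and baseline within each arm";
- a longitudinal model: "repeated measures modeling based on mixed models will be conducted to compare outcome variables between two arms".

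None is ranked above the others. The Primary Aim in Specific Aims likewise covers both contrasts: "We will explore differences within each arm and compare the 2 intervention arms". The Hypothesis below it predicts significant improvement, including in weight loss, without naming a comparator.

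**The concern.** The reason to randomise against Enhanced Usual Care is to remove whatever would have happened to weight anyway: time trend, regression to the mean, the effect of being measured and paid to attend. A pre-post test within one arm removes none of this. If both arms lose weight for shared reasons, MTG looks effective; if both gain, a real effect can be hidden.

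The plan does include the randomised comparison, so the problem is one of priority and power. With three weight analyses and no order among them, a reader cannot tell which one answers the randomised question. A significant within-arm result would satisfy the hypothesis as worded. The two printed power figures, 82% and 80%, suggest adequate power throughout. The first does not follow from its inputs, and the second applies to a larger difference than the smallest one the assumed arm means imply. The pilot is meant to prepare a larger trial, for which the arm difference and its precision are the useful results.

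**Working it through.** **Inputs** (all from Sample Size and Power Analysis): n = 60 evaluable per arm; mean change −2.3 kg in MTG and 0 in Enhanced Usual Care; SD of change 5.3 kg, taken as common to both arms; two-sided α = 0.05. Power is from the noncentral t distribution. For the rank tests, n is multiplied by 3/π = 0.955, their asymptotic efficiency under normality.

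**1. The stated within-arm 82%.** Noncentrality = (2.3/5.3) × √60 = 3.36; critical t on 59 df = 2.00.

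| Test | Power |
|---|---|
| Paired t | 91.1% |
| Wilcoxon (effective n = 57.3) | 89.8% |
| Stated in the plan | 82% |

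Simulation of 20,000 normal trials agrees (90.9% and 89.5%). The 82% would need about 46 patients (paired t) or 48 (Wilcoxon), a change of 2.0 kg at n = 60, or an SD of change of about 6.1 kg. None of these is in the text, and its source cannot be established from the documents. At the zero change assumed for Enhanced Usual Care, the rejection rate is simply α, 5%, so a power claim for each arm contradicts the assumptions.

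**2. The stated between-arm 80% at 2.8 kg.** SE of the difference = 5.3 × √(2/60) = 0.968 kg; noncentrality = 2.8/0.968 = 2.89. Power is 81.9% (t) or 80.1% (Mann-Whitney). This figure reproduces. So does the dropout allowance: 120/0.75 = 160.

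**3. Between-arm power at the implied difference.** 0 − (−2.3) = 2.3 kg; noncentrality = 2.3/0.968 = 2.38; critical t on 118 df = 1.98.

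| True difference | Two-sample t | Mann-Whitney |
|---|---|---|
| 2.3 kg | 65.5% | 63.4% |
| 2.8 kg | 81.9% | 80.1% |

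Simulated values at 2.3 kg are 65.7% and 63.5%. The 95% CI half-width is 1.98 × 0.968 = 1.92 kg. The difference detectable with 80% power is 2.73 kg (t) or 2.80 kg (Mann-Whitney).

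**4. Effect of baseline adjustment.** The documents give no correlation. If covariates correlate 0 to 0.4 with weight change (an assumption), the residual SD is 5.3 × √(1 − r²), and t-test power at 2.3 kg runs from 65% to 73%.

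**5. What a shared change does to the within-arm test.** The shared changes below are assumptions chosen for illustration. The 2 kg gain has the size of the yearly pre-enrolment gain that the Background cites for MOVE! participants; it is not a forecast for this trial. The third column is the chance of a significant pre-post loss in MTG (paired t, n = 60).

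| Scenario | Mean MTG change | Significant loss in MTG |
|---|---|---|
| No effect, both arms lose 1.0 kg | −1.0 | 30% |
| No effect, both arms lose 2.0 kg | −2.0 | 82% |
| 2.3 kg effect, both arms gain 1.0 kg | −1.3 | 46% |
| 2.3 kg effect, both arms gain 2.0 kg | −0.3 | 6% |

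In the last two rows between-arm power stays at 65%, because the shared change cancels.

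**The case against.** The strongest reply is that this is a pilot with an exploratory aim, it already plans the randomised comparison more than once, and it openly says the between-arm effect is unknown and gives a detectable difference instead. That is an ordinary approach for a pilot, and the 2.8 kg figure is right. The 65% is also power at a floor, since the plan assumes a loss of at least 2.3 kg: by t-test it would be 73% at 2.5 kg and 87% at 3.0 kg, and baseline adjustment could raise it. The 82% error understates power, so the trial is not too small for the test that sized it.

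Much of this stands, and it limits how serious the point is. Nothing in the documents says efficacy will be judged on within-arm tests alone, and the shared-change scenarios are illustrations that should not drive the severity.

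It does not remove the point. Calling the between-arm effect unknown sits badly with assuming a mean for each arm in the same paragraph; once both are assumed, their smallest implied difference deserves a power figure. The plan makes formal power claims and predicts significant improvement, so those claims should be correct and attached to the comparison that randomisation supports.

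**Conclusion.** The concern holds and should be fixed. The within-arm power follows from the plan's own inputs as about 91% (paired t) or 90% (Wilcoxon), not 82%, and has no meaning for an arm assumed not to change. Between-arm power at the smallest difference implied by the assumed means is about 65% (t) or 63% (Mann-Whitney) and is not reported; the reported 80% at 2.8 kg is correct. No weight analysis is given priority, while the sizing rests on a contrast that cannot isolate the effect of MTG.

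These figures assume 60 evaluable patients per arm, a common SD of 5.3 kg, approximately normal changes and no covariate adjustment. The faults concern reporting and priority; the number of patients need not change.

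**What to change.** 1. **Analysis plan.** Suggested text: *The main weight analysis is the MTG minus Enhanced Usual Care difference in weight change from baseline to 12 months, estimated from the mixed model (arm-by-visit term) with a 95% confidence interval. Mann-Whitney tests at each visit are supportive; within-arm tests are descriptive.*
2. **Hypothesis.** Add that improvement is relative to Enhanced Usual Care.
3. **Sample size.** Name one test. Suggested text: *With 60 evaluable per arm and SD 5.3 kg (two-sample t-test, two-sided 0.05, unadjusted), power is 65% for a 2.3 kg difference, the smallest implied by these assumptions, and 82% for 2.8 kg; the 95% confidence interval half-width is about 1.9 kg. Baseline adjustment may raise this power.* The plan does not say which test gave its 80%; if Mann-Whitney is used for sizing, state 63% and 80% instead. Either is an unadjusted approximation for the mixed model.
4. **Within-arm figure.** Replace 82% with 91% (paired t) for the MTG arm only, or drop it.

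Keep 160 randomised. The cost is wording: no added patients, visits or analyses, since the mixed model is already planned. The downside is a less favourable stated power, 65%, for the main comparison.
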